7.10 Progression free survival (PFS)

PFS is defined as the time from first day of protocol therapy to disease progression, death due to any cause or last subject contact. PFS is defined for all subjects entered on the study, following an intent-to-treat analysis plan. A secondary analysis will also include a calculation of PFS from day of rituximab infusion.

7.11 Overall Survival (OS)

Overall survival is defined as the time from first day of protocol therapy to death due to any cause or last subject contact.

7.12 Safety evaluation

Data from all subjects who receive any study drug will be included in the safety analyses. Subjects who entered the study and did not take any of the study drug(s) and had this confirmed, will not be evaluated for safety.

The severity of the toxicities will be graded according to the NCI CTCAE v3.0 whenever possible.

8 Statistical Plan

Statistical design and analysis

Design. This study will enroll 45 evaluable subjects, all of whom have had lymphoma progression or failure to respond within six months of being treated with rituximab alone or with a rituximab-containing regimen. Twenty-five patients will be enrolled into Cohort 1, which will consist of daily dosing of lenalidomide and weekly dosing of dexamethasone. An additional twenty patients will be enrolled into Cohort 2, in which patients will receive daily dosing of lenalidomide, but will not be treated with weekly dexamethasone. Subjects with documented Rituxan-refractory disease will be enrolled to the study and treated for two 28-day cycles with lenalidomide – dexamethasone (Cohort 1) or lenalidomide alone (Cohort 2). After this first treatment period, termed Part I, subjects will be re-evaluated and subsequently treated with

lenalidomide – dexamethasone and rituximab (Cohort 1) or lenalidomide and rituximab (Cohort 2) in combination. A subject who does not complete rituximab therapy as part of this study will be considered non-evaluable and may be replaced by enrolling an additional subject. However, all subjects will be included in the intent-to-treat analysis.

Power to detect adverse effects. With 45 subjects, we will have 90% power to detect any unforeseen toxicity whose prevalence is at least 5.0%. The half-width of the confidence interval for any fraction (toxicity or response) will extend no more than +/- 15% around the estimate.

Treatment response. We will use McNemar's test to compare the fractions of patients responding to rituximab therapy without (baseline) and with revlimid. In the baseline period, we estimate that 10% of patients will have responded to rituximab, although all will ultimately fail within 6 months. Assuming a modest kappa (intra-subject correlation) of 10%, with 45 patients we have 87% power to detect a significant effect of revlimid treatment if the treatment-period response rate is 35%.

Time to progression. We will compute a 95% confidence interval for the ratio of median TTP under revlimid+rituximab to the median TTP under rituximab alone, using the nonparametric method of Jung and Su (1995). If the interval excludes 1, we will declare the difference to be statistically significant.

To evaluate the power of this design, we assumed that TTP in the baseline (rituximab only) period would be statistically independent of TTP in the follow-up (combination treatment) period. This will lead to a conservative estimate of the power, as positive correlation of failure-time endpoints generally increases power for paired comparisons (e.g., see Mick et al. 2000). Assuming that median TTP in the baseline period is 3 months, we calculated the power to detect significance in a test of the null hypothesis that median TTP is the same in both periods. If the median TTP in the follow-up period is doubled, to 6 months, then the power is 83%; if the median TTP is tripled, to 12 months, then the power is essentially 100%. Thus power is satisfactory if there is a substantial increase in the median TTP.

Design and analysis of correlative studies. In correlative studies, we will compare mean changes in immunologic phenotype parameters (fraction Th2⁺ cells, NK cells and Treg cells) between the subjects who experience a remission (expected to be up to 80%, or 36 of 45 subjects) and those who do not (as few as 20%, or 9 of 45 subjects). As we do not yet know the likely values of these immunologic parameters, we estimate the power in terms of the difference in means as a fraction of the common standard deviation (SD). The basic analysis is a t test comparing mean change in the two groups. Calculations show that if the standardized difference is equal to 1 SD, then the power is 75%, whereas if the standard difference is 1.25 SDs, then the power is 91%. Thus the power of this correlative analysis is reasonable as long as there is a reasonably large difference in mean change between the remission and non-remission groups.

Analysis of serum albumin as a biomarker. We will test the hypotheses that 1) a decrease in serum albumin by ≥ 0.3 g/dL at commencement of cycle 2 from baseline predicts a response (CR/PR) to protocol therapy and that 2) a baseline serum albumin ≤ 4.1 g/dL predicts no response (SD/PD) to protocol therapy. From preliminary analysis of our first eleven patients, we will assume the same breakdown of responses (3 non-responders: 8 responders). Using this

assumption, we will have 80% power with a two-tailed alpha of 0.05 to detect an odds ratio of 2.6; this is 10 times less than expected.

9 Safety and Adverse Events

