2.2 Secondary Objectives

- 2.2.1 To determine time to progression after lenalidomide + rituximab therapy with and without dexamethasone in relapsed small B-cell lymphomas with rituximab resistance and compare the time to progression for the previous rituximab-containing regimen
- 2.2.2 To compare the response rate for the previous rituximab-containing regimen to that obtained subsequently to lenalidomide + rituximab therapy with and without dexamethasone.
- 2.2.3 To determine the toxicity profile of lenalidomide + rituximab therapy with and without dexamethasone in patients who have received a previous rituximab-containing combination regimen.
- 2.2.4 To correlate Fc γ RIIIa receptor polymorphism profiling with response to lenalidomide - dexamethasone + rituximab therapy in relapsed small B-cell lymphomas with rituximab resistance (Cohort 1 only).
- 2.2.5 To evaluate changes in NK cells, activated NK cells, activated T cells, T regs, and several plasma cytokines following exposure to lenalidomide - dexamethasone and lenalidomide - dexamethasone + rituximab therapy and correlation of observed changes to objective response rates.

[figure not shown]
2.2.6 To determine the presence or absence of minimal residual disease after Part I and Part II of protocol therapy using a PCR-based assay of DNA.

2.2.7 To determine whether 1) a decrease in serum albumin by ≥ 0.3 g/dL at commencement of cycle 2 from baseline predicts a response (CR/PR) to protocol therapy and whether 2) a baseline serum albumin ≤ 4.1 g/dL predicts no response (SD/PD) to protocol therapy.

3 Study Design

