4.1 Inclusion Criteria

- **Documentation of disease**
 - Previously treated, histological confirmed follicle center lymphoma, grade 1-3a, marginal zone lymphoma, small lymphocytic lymphoma with < 5000 lymphocytes /mm³ or lymphoplasmacytic lymphoma with <3gm/ml IgM, mantle cell lymphoma by WHO classification (see Appendix F).
 - Bone marrow biopsies as sole means of diagnosis are not acceptable. Fine needle aspirates are not acceptable.
 - Institutional flow cytometry or immunohistochemistry must document CD20 antigen expression. Past documentation of CD20 antigen expression is admissible.
- **Prior treatment**
 - Patients must have been treated with rituximab in combination with chemotherapy or as monotherapy and must have refractory or progressive disease. Subjects must have had less than a partial response or progressive disease within 6 months of any dose of rituximab.
- Age ≥ 18
- ECOG performance status 0-2 (see Appendix B)
- Measurable disease must be present either on physical examination or imaging studies. Non-measurable disease alone is not acceptable. Any tumor mass $> 2\text{cm}$ is considered measurable.
- Lesions that are considered non-measurable, but assessable include the following:
 - Bone lesions (lesions if present should be noted)
 - Ascites
 - Pleural/pericardial effusion
 - Lymphangitis cutis/pulmonis
 - Bone marrow (involvement by non-Hodgkin lymphoma should be noted)
- Patients with a history of intravenous drug abuse or any behavior associated with increased risk of HIV infection should be tested for exposure to the HIV virus.

- Understand and voluntarily sign an informed consent form.
- Able to take aspirin (81 or 325 mg) daily as prophylactic anticoagulation. Patients intolerant to ASA may use warfarin or low molecular weight heparin
- Laboratory test results within these ranges:
 - Absolute neutrophil count $\geq 1000/\text{mm}^3$
 - Platelet count $\geq 75,000/\text{mm}^3$
 - Serum creatinine $\leq 2.0 \text{ mg/dL}$
 - Total bilirubin $\leq 1.5 \text{ mg/dL}$ (unless due to Gilbert's syndrome)
 - AST (SGOT) and ALT (SGPT) $\leq 2.5 \times \text{ULN}$ or $\leq 5 \times \text{ULN}$ if hepatic metastases are present.
- Disease free of prior malignancies for ≥ 5 years with exception of currently treated basal cell or squamous cell carcinoma of the skin, or carcinoma "in situ" of the cervix or breast.

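### McNemar's test compares on-study response with a prior response lowered by selection, so its null is not the null of no lenalidomide effect and the 87% is not power for one

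*Combined protocol and SAP*

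**What the plan says.** Section 4.1 sets the entry rule: "Subjects must have had less than a partial response or progressive disease within 6 months of any dose of rituximab". Sections 3.1 and 8 repeat it in substance. Prior rituximab may have been given alone or with chemotherapy.

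Section 8 (Treatment response) names the test: "We will use McNemar's test to compare the fractions of patients responding to rituximab therapy without (baseline) and with revlimid". It gives the baseline assumption: "In the baseline period, we estimate that 10% of patients will have responded to rituximab, although all will ultimately fail within 6 months". The power statement follows: "Assuming a modest kappa (intra-subject correlation) of 10%, with 45 patients we have 87% power", described as "power to detect a significant effect of revlimid treatment if the treatment-period response rate is 35" per cent. No alpha or sidedness is stated for this test.

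The test serves secondary objective 2.2.2: "To compare the response rate for the previous rituximab-containing regimen to that obtained subsequently to lenalidomide + rituximab therapy with and without dexamethasone". The primary objective (2.1.1) is the response rate itself. The Study Summary also lists McNemar's test.

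Three further items bear on the comparison. Cohort 1 (25 of the 45 patients) receives dexamethasone as well as lenalidomide. Section 7.8.2 counts stable disease as a response at the evaluation 3 months after rituximab. Section 7.8.1 (Part I response) does not, and the albumin analysis in Section 8 classes stable disease as non-response.

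**The concern.** Patients are admitted because rituximab failed, and that course, or one close to it, then supplies the control rate. A rate observed in people chosen for a poor outcome need not be the rate they would show if treated again. If re-treatment alone would do better than the selected rate, that improvement is counted in favour of lenalidomide.

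McNemar's null is that the on-study rate equals the prior rate. Section 8 reads rejection as an effect of lenalidomide. That reading needs one more premise, that rituximab alone would again produce the prior rate, and the plan neither states nor supports it. Even a real difference could not be assigned to lenalidomide alone, because 25 of 45 patients also receive dexamethasone and the prior regimen may have included chemotherapy.

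What is at stake is the claim that lenalidomide overcomes rituximab resistance. This is the only response comparison for which Section 8 gives a power.

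**Working it through.** **Inputs from Section 8.** n = 45, prior rate p1 = 0.10, on-study rate p2 = 0.35, kappa = 0.10, stated power 87%. **Assumed:** two-sided alpha 0.05, which Section 8 states only for the albumin analysis ("80% power with a two-tailed alpha of 0.05 to detect an odds ratio of 2.6").

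**Step 1: the 2×2 cells.**
- Chance agreement: p1·p2 + (1−p1)(1−p2) = 0.10×0.35 + 0.90×0.65 = 0.62.
- Observed agreement: 0.62 + 0.10×(1−0.62) = 0.658, so the discordant probability is 0.342.
- The discordant cells differ by p2−p1 = 0.25. On-study only = (0.342+0.25)/2 = 0.296; prior only = (0.342−0.25)/2 = 0.046.

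**Step 2: reproduce the power.** Let b and c be the on-study-only and prior-only counts. Reject when (b−c)²/(b+c) ≥ 3.84. Sum over b+c ~ Binomial(45, 0.342) and, given that total, b ~ Binomial(b+c, 0.296/0.342), counting rejections with b > c. The result is **87.3%**, which matches the plan. Exact two-sided McNemar gives 81.7% and the continuity-corrected test 80.4%, so the plan's figure fits the uncorrected test.

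**Step 3: same test, no lenalidomide effect.** Set p2 to the response that rituximab re-treatment would give without lenalidomide. The documents do not state this for refractory patients, so it is an assumed range. The table gives the probability of declaring a benefit; the nominal value in this direction is 2.5%.

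| Assumed no-lenalidomide rate | Prior rate 10%, uncorrected | Prior rate 10%, exact | Prior rate 15%, uncorrected |
|---|---|---|---|
| 5% | 0.2% | <0.1% | <0.1% |
| 10% | 2.3% | 0.8% | 0.3% |
| 15% | 10% | 6% | 2% |
| 20% | 26% | 19% | 8% |
| 25% | 49% | 39% | 22% |
| 30% | 71% | 63% | 42% |

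**Step 4: is 10% fixed by entry?** No. A responder who progressed within 6 months is eligible. As an illustration only, take the two rituximab results in Section 1.1 and assume exponential time to progression.
- 48% response, median 12 months: the share of responders progressing by 6 months is 1−2^(−6/12) = 0.293. The prior rate among eligible patients is 0.48×0.293/(0.52+0.48×0.293) = 21%.
- 40% response, median 18 months: 1−2^(−6/18) = 0.206, and 0.40×0.206/(0.60+0.40×0.206) = 12%.

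Selection lowers 48% to 21% and 40% to 12%, but does not pin the rate at 10%. With a 21% prior rate, the uncorrected test declares a benefit in 0.3%, 2%, 6% and 17% of trials at no-lenalidomide rates of 15%, 20%, 25% and 30%.

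**The case against.** The strongest reply has four parts.

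*The test does what its objective asks.* Objective 2.2.2 is a comparison with the previous regimen, and McNemar's test makes that comparison. The primary objective is the response rate, and Section 8 already plans a confidence interval for response fractions. This stands. It limits the point to the causal reading and the power statement.

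*Resistance may be stable.* If refractory patients would again respond at the prior rate, the null is the right one and the error is 2.3%. This cannot be excluded. But the plan gives no evidence for it, and its own planning assumptions (kappa of 0.10, and independent times to progression in the two periods) treat prior outcome as a weak guide to later outcome. Those assumptions concern treated patients, so they weaken the defence without disproving it.

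*The bias may run the other way.* Section 1.1 reports lower response after three or more chemotherapy regimens, and the prior course may have contained chemotherapy that the study regimen lacks. If re-treatment would give 5% against a prior 10%, the test is conservative (0.2%). This stands. Nor does the 40% re-treatment rate in Section 1.1 settle the direction, since it comes from patients whose first response lasted at least 6 months.

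*Some inferences go too far.* A reader might infer that the entry criteria hold the baseline near 10%. They do not: early-progressing responders are eligible and Section 8 calls 10% an estimate. A reader might also infer that prior response is taken from routine records and so measured differently. The plan does not say how it is ascertained, so that is a gap at most, and the argument does not need it.

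**Conclusion.** The point holds as a limit on interpretation. The arithmetic behind the 87% is sound, but it is power to detect a difference from a prior rate lowered by selection, not power to detect an effect of lenalidomide.

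The chance of a false claim of benefit depends on two quantities that the documents do not establish: the actual prior rate and the no-lenalidomide re-treatment rate. With a 10% prior rate it is 2.3% if re-treatment gives 10%, and 10% to 71% if re-treatment gives 15% to 30%. With a 15% prior rate the last range becomes 2% to 42%. Exact McNemar gives lower figures. All of these assume n = 45, kappa 0.10 and two-sided 0.05.

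A reader might infer that the test is bound to produce a false positive, or that its error rate is known to be inflated. The documents support neither. They show that the error rate for the lenalidomide claim is not controlled by the design and that its direction is unknown. The primary response-rate estimate does not depend on this test.

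**What to change.** - In Section 8, base the response conclusion on the primary on-study response rate with an exact 95% confidence interval.
- Keep McNemar's test for objective 2.2.2, labelled as a descriptive comparison with the previous regimen. State its alpha, sidedness and form (exact or uncorrected), and define which prior course is the baseline, since entry refers to any rituximab dose and the objective to the previous regimen.
- Replace the wording that attributes a significant result to lenalidomide with: *a difference from the prior-regimen response rate in patients selected for rituximab failure*. Restate the 87% in the same terms.
- Use CR/CRu/PR in both periods for this comparison, and reconcile Section 7.8.2, which counts stable disease as response. Otherwise a patient with stable disease both times could be scored as improved.
- Make matching edits to the McNemar entry in the Study Summary, and check that objective 2.2.2 is read as a comparison with the prior regimen only.

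No change to sample size, visits or data collection follows from the relabelling. The response definition is more than a wording edit, because it changes how an endpoint in Section 7.8.2 is counted and should be settled before analysis. The price is a weaker causal claim from the same data.

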7.8 Response Rates

- 7.8.1 ***Response to Lenalidomide with and without Dexamethasone:*** Response rate is defined as the percentage of subjects who attain complete response (CR), complete response unconfirmed (CRu), or partial response (PR) after two cycles of –study treatment (lenalidomide-dexamethasone for Cohort 1 subjects; lenalidomide monotherapy for Cohort 2 subjects. Subjects may be scored as having progressive disease (PD) after 2 cycles of –study treatment and will be removed from the study if the estimated life expectancy is < 3 months at that time. Following an intent-to-treat analysis plan, all subjects who receive one day of chemotherapy will be included in the denominator for this response rate.
- 7.8.2 ***Response to Lenalidomide + Rituximab with and without Dexamethasone:*** Response to lenalidomide plus rituximab with and without dexamethasone is defined as the percentage of subjects in complete remission (CR), complete remission unconfirmed (CRu), partial response (PR), or with stable disease (SD) at the 3 months post-rituximab evaluation. Only subjects who receive rituximab are included in the denominator for this secondary response rate.

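### The McNemar comparison for objective 2.2.2 does not score the prior and on-study periods by one response rule, so its bias can run either way and the 87% power is not tied to a defined outcome

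*Combined protocol and SAP*

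**What the plan says.** Secondary objective 2.2.2 is "To compare the response rate for the previous rituximab-containing regimen to that obtained subsequently to lenalidomide + rituximab therapy", with and without dexamethasone. Section 8 (Treatment response) gives the method: "We will use McNemar's test to compare the fractions of patients responding to rituximab therapy without (baseline) and with revlimid".

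For the prior regimen, Section 8 states that "we estimate that 10% of patients will have responded to rituximab, although all will ultimately fail within 6 months". It names no response categories and no assessment time. The inclusion criteria (Section 4.1) admit patients who fell short of a PR on rituximab or who progressed within six months of a dose. Under Section 7.4, SD is less than a PR, so SD on prior rituximab is a failure at entry.

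For the study period, the power statement is conditional: "Assuming a modest kappa (intra-subject correlation) of 10%, with 45 patients we have 87% power" to detect an effect "if the treatment-period response rate is 35"%. Section 8 does not say what counts as a response in that 35%. The only definition of response to the combination is Section 7.8.2, which counts CR, CRu, "partial response (PR), or with stable disease (SD) at the 3 months post-rituximab evaluation", among subjects who receive rituximab. Section 3.1 places that scan at about month 5, before Cycle 6.

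**The concern.** McNemar's test compares two margins of the same yes/no outcome in the same patients. It is informative only if one rule produces both margins. Here the rules differ in two ways.

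- **Timing.** A prior response that was later lost still counts. An on-study response lost before the 3-month scan does not. This lowers the on-study rate relative to the prior rate.
- **Stable disease.** A patient with SD throughout is a failure on the prior regimen and a responder on study under 7.8.2. This raises the on-study rate relative to the prior rate.

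A significant result for objective 2.2.2 could therefore reflect the change of definition and not an effect of lenalidomide, and a null result could partly reflect the timing. With no rule fixed in Section 8, the choice could also be made after the data are seen.

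**Working it through.** **Inputs.** From Section 8: N = 45 pairs, prior rate 10%, on-study rate 35%, kappa 0.10, stated power 87%, median TTP of 3 months in the baseline period. From Sections 3.1 and 7.8.2: scan 3 months after the first rituximab dose, about month 5. No alpha is given for McNemar's test. I assume two-sided 0.05, the level stated for the albumin analysis ("we will have 80% power with a two-tailed alpha of 0.05").

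**Step 1: reproduce the 87%.** With margins p1 (prior) and p2 (on study):

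- Chance agreement: p1·p2 + (1−p1)(1−p2) = 0.035 + 0.585 = 0.620.
- Observed agreement at kappa 0.10: 0.620 + 0.10 × 0.380 = 0.658, so discordance is 0.342.
- Responder on study only: (0.342 + 0.25)/2 = 0.296. Responder on prior only: (0.342 − 0.25)/2 = 0.046.

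Enumerating all discordant counts for N = 45 gives 87.3% for the uncorrected test, which matches the plan. The exact conditional version gives 81.7% and the continuity-corrected version 80.4%; the plan does not name a version.

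**Step 2: is the 10% on the 7.8.2 scale?** A median TTP of 3 months means that half the patients have not progressed at 3 months. Scored as CR, CRu, PR or SD three months after the TTP clock starts, the prior regimen would therefore show about 50%, not 10%. The 10% must refer to something narrower than 7.8.2.

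**Step 3: no gain in TTP, on study scored by 7.8.2.** Assume exponential TTP with the same 3-month median on study. The share progression-free at the scan is:

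- clock starting at rituximab: 0.5^(3/3) = 50%;
- clock starting at first protocol therapy: 0.5^(5/3) = 31.5%.

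**Step 4: timing alone.** Suppose that 35% is an ever-response rate, SD is not counted, and the CR/CRu/PR rate at the scan is 30% or 25%.

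Results, each against a prior rate of 10% with N = 45, kappa 0.10 and the uncorrected two-sided test:

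| On-study rate | Scenario | On study only | Prior only | Probability of significance |
|---|---|---|---|---|
| 35% | plan's figure | 0.296 | 0.046 | 87.3% |
| 30% | timing loss, SD excluded | 0.253 | 0.053 | 71.3% |
| 25% | timing loss, SD excluded | 0.210 | 0.060 | 48.8% |
| 31.5% | no TTP gain, SD counted | 0.266 | 0.051 | 76.9% |
| 50% | no TTP gain, SD counted | 0.425 | 0.025 | 99.8% |

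**Step 5: how the two differences offset.** If CR/CRu/PR at the scan is 28%, power is 62.8%. Adding SD in a further 7% of patients gives 28% + 7% = 35% and restores 87.3%. SD in 10% gives 38% and 93.2%.

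**The case against.** Section 8 does not cite 7.8.2, and reading the prior rate as response at any time is an inference from its wording. On this view the plan is silent, not contradictory. That is fair as far as it goes. But 7.8.2 is the only definition of response to the combination, and Section 7.8.1 is assessed before any on-study rituximab. An analyst following the document would arrive at 7.8.2, and Step 2 shows that the 10% cannot be on that scale.

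A reader might infer something stronger: that an on-study patient counts only if still in response at the scan, that the mismatch works against the combination, and that the 87% power is lost. The documents do not support this. Section 7.8.2 also counts SD, which pushes the other way. The 87% reproduces, and a loss needs two assumptions that the plan does not make: that 35% is an ever-response rate and that SD is excluded. If 35% is already the rate at the scan, nothing is lost on the study side.

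The best objection concerns the remedy. Rituximab starts in Cycle 3, after the Part I restaging, and no imaging restaging is scheduled between that and the pre-Cycle 6 scan. On scheduled imaging, best response therefore differs from CR/CRu/PR at the scan only by adding Part I responses since lost, all first seen before on-study rituximab. Section 1.4 aims at reversal of rituximab resistance, so scoring such a patient as a non-responder is defensible. This stands, and it is why the fix must state the choice openly and report the 3-month result beside it.

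**Conclusion.** The point holds as a defect of definition. The two margins follow different rules on both timing and SD, and the 10%, 35% and 87% are not tied to a stated outcome.

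The net bias is undetermined. It may be a false positive: about 77% to 99.8% probability of significance with no TTP gain, if the analyst uses 7.8.2 on study and if TTP is exponential with a 3-month median and kappa is 0.10. It may be a loss of power, to 71% or 49%, if 35% is an ever-response rate, SD is excluded and the rate at the scan is 30% or 25%. These figures show the size of each effect; they do not predict the result. Under one CR/CRu/PR rule with rates of 10% and 35%, power remains 87.3%, so the design itself does not need to change.

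**What to change.** In Section 8, for the McNemar test only:

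1. Count CR, CRu or PR, and not SD, as response in both periods.
2. Use one timing rule: best documented response on the prior rituximab-containing regimen, and best response up to and including the 3-month post-rituximab evaluation on study.
3. State that the on-study result describes the whole regimen, because it can include Part I responses seen before rituximab.
4. Report CR/CRu/PR at the 3-month scan as a sensitivity analysis. Set against best prior response, it is the stricter test of the combination.
5. Keep 7.8.2 as a descriptive rate.
6. State that the 10%, 35% and 87% refer to the chosen definition, and give the alpha, sidedness and version of the test. Name the denominator too: 7.8.2 uses subjects who receive rituximab, while Section 8 puts all subjects in the intent-to-treat analysis.

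Applying 7.8.2 to both periods would also be consistent, but it needs a prior-regimen status at a fixed 3 months, which the plan does not arrange to collect. With medians of 3 and 6 months (exponential, clock at rituximab), it would compare 50% with 0.5^(3/6) = 70.7%, at 57% power.

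The cost is SAP wording. Both on-study scans are already scheduled. Prior best response has to come from the chart, as any scoring of the prior regimen does. The trade-off is that the main comparison no longer isolates response after rituximab; items 3 and 4 make that visible.

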7.9 Time to progression (TTP)

TTP is defined as the time from the first day of protocol therapy to the first event defining progression of disease or last subject contact. TTP is defined for all subjects receiving protocol therapy, following an intent-to-treat analysis plan. TTP from rituximab is defined for patients receiving rituximab (Part II) from the first day of rituximab therapy to the first event defining treatment failure.

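### A TTP ratio interval that excludes 1 does not by itself show a lenalidomide benefit, because patients enter the trial by having failed early on prior rituximab

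*Combined protocol and SAP*

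**What the plan says.** The Time to progression paragraph of Section 8 plans a 95% interval for the "ratio of median TTP under revlimid+rituximab to the median TTP under rituximab alone", with the rule "If the interval excludes 1, we will declare the difference to be statistically significant". The pairing is within patient: secondary objective 2.2.1 is to determine TTP on study and "compare the time to progression for the previous rituximab-containing regimen". The Study Summary describes the same paired comparison.

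Four other places bear on how the result can be read:

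- **Entry (Section 4.1):** "Subjects must have had less than a partial response or progressive disease within 6 months of any dose of rituximab".
- **Planning premise (Section 8, Treatment response):** "we estimate that 10% of patients will have responded to rituximab, although all will ultimately fail within 6 months".
- **On-study TTP (Section 7.9):** "time from the first day of protocol therapy to the first event defining progression of disease or last subject contact", with no upper limit.
- **Cohorts (Section 3.1):** both receive lenalidomide plus rituximab and differ only in dexamethasone.

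The power statement begins "Assuming that median TTP in the baseline period is 3 months", treats the two periods as independent, and gives 83% power for a doubling to 6 months and near-certain power at 12 months. Its null is that the median is the same in both periods. No caveat, adjustment or sensitivity analysis for selection appears in the documents.

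**The concern.** This is regression to the mean. The denominator of the ratio comes from patients chosen because that TTP, or the response that goes with it, was poor. The numerator comes from the same patients without any such restriction. Unless a patient's TTP is nearly the same from one line to the next, or shortens with each line, the second median will tend to exceed the first even if lenalidomide adds nothing.

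The plan labels the two medians by drug, and the Study Summary gives the aim as evaluating lenalidomide's potential to overcome rituximab resistance. A report that follows the rule could therefore present a statistically significant gain in TTP as a drug effect when part or all of it comes from who was enrolled.

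**Working it through.** **Inputs from the documents.** 45 pairs; two-sided 95% interval; baseline median 3 months; all baseline failures within 6 months (Section 8); entry rule (Section 4.1); uncapped on-study TTP (Section 7.9).

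**Assumptions, because the documents give no figure.** The TTP distribution, the effective cap on prior TTP, the within-patient correlation and any later-line decline. There is no censoring and no drug effect throughout.

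**1. The plan's own figure.** The 83% cannot be rebuilt, since neither distribution nor censoring is stated. With exponential TTP, the standard error of the log ratio is √(2/(45 × (ln 2)²)) = 0.304, and ln 2/0.304 − 1.96 = 0.32, which gives 62.5% power. A Weibull shape of about 1.28 would give 83%. The figure is not called wrong, and nothing below depends on it.

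**2. The no-effect ratio.** Let F be the unselected TTP distribution, with median M. Under a cap C on prior TTP, the baseline median t solves F(t) = 0.5 × F(C). With independent periods and no drug effect, the on-study median is M, so the ratio is M/t.

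For an exponential, set t = 3 and x = 2^(−3/M).

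- C = 6: 1 − x = (1 − x²)/2 reduces to x = 1, so no finite M works. An exponential cannot meet Section 8's two statements (median 3 months, all failing by 6). A Weibull with rising hazard can.
- C = 9: the condition reduces to x² + x = 1, so x = 0.618, M = 4.32 and the ratio is 4.32/3 = 1.44.

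Caps above 6 months are relevant because the entry clock runs from any dose, so TTP counted from the start of the regimen can be longer than 6 months.

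**3. Scenarios matched to t = 3 months.** ρ is the within-patient correlation (Gaussian copula). The last two columns give the share of simulated trials whose interval lies wholly above 1 (nominal 2.5%).

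| Scenario | M | Ratio, ρ = 0 | Ratio, ρ = 0.6 | Above 1, ρ = 0 | Above 1, ρ = 0.6 |
|---|---|---|---|---|---|
| Exponential, cap 7 | 8.37 | 2.79 | 1.43 | 95% | 27% |
| Exponential, cap 8 | 5.31 | 1.77 | 1.18 | 52% | 10% |
| Exponential, cap 9 | 4.32 | 1.44 | 1.09 | 24% | 4% |
| Exponential, cap 12 | 3.41 | 1.14 | 1.02 | 6% | 2% |
| Weibull 1.2, cap 6 | 7.58 | 2.53 | 1.39 | 97% | 33% |
| Weibull 1.3, cap 6 | 5.54 | 1.85 | 1.22 | not run | not run |
| Weibull 1.5, cap 6 | 4.06 | 1.35 | 1.09 | 33% | 6% |
| Weibull 2.0, cap 6 | 3.20 | 1.07 | 1.01 | 5% | 2% |

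The rates come from 2,000 simulated trials of 45 pairs each, so the simulation error is at most √(0.5 × 0.5/2000), about 1 percentage point. A paired percentile bootstrap (400 resamples) stands in for the plan's named interval method. Without selection it lies wholly above 1 in 1.9% of trials (ρ = 0) and 1.1% (ρ = 0.6), so the stand-in does not produce the excess.

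**4. Entry by less than a partial response.** Suppose the 6-month limit binds only the progression route and a fraction q enters with no limit on prior TTP. Then (1 − q) × F(3)/F(6) + q × F(3) = 0.5. For q = 25%, 50% and 75%, M = 6.67, 4.32 and 3.46, and the ratios at ρ = 0 are 2.22, 1.44 and 1.15.

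**5. Strict 6-month cap, exponential, not matched to 3 months.** Unselected medians of 3, 6 and 9 months give baseline medians of 2.03, 2.49 and 2.66. The ratios are 1.47, 2.41 and 3.39 at ρ = 0, and 1.10, 1.34 and 1.56 at ρ = 0.6.

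**6. Later-line decline.** If the unselected median falls to a fraction d of its earlier value, the ratio is multiplied by d, so the bias cancels at d = 1/ratio. For caps 7, 8, 9 and 12 this is 36%, 56%, 69% and 88% at ρ = 0, and 70%, 85%, 91% and 98% at ρ = 0.6. A larger fall reverses the bias: with cap 9, ρ = 0 and TTP halved, 1.44 × 0.5 = 0.72.

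**The case against.** The strongest reply is that the plan claims little. Its stated null is equality of the two period medians, the interval tests that validly, and explicit wording about a treatment effect appears in the response paragraph rather than the TTP one. This is true of the arithmetic. It does not settle the reading, because the TTP paragraph names the medians by drug and the trial's aim is to show that resistance is overcome.

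The second reply concerns size, and much of it stands. The large figures need independent periods, which the plan adopts only to keep its power estimate conservative. At ρ = 0.6 the matched ratios are 1.01 to 1.43, and at 0.8 they are 1.00 to 1.13. With ρ = 0.6 and an assumed 20% later-line decline, the interval lies wholly above 1 in 0 to 7% of trials. These correlations and declines are also assumptions, however, and the plan states neither.

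Third, the cut is not clean. Less than a partial response includes long stable disease, and the qualifying failure need not have been on the regimen being compared. This softens the bias. Steps 2 and 4 allow for part of it, but a mismatch of regimens was not modelled.

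Finally, this is a secondary objective in an uncontrolled phase II trial, and one interpretive sentence might be enough. That is close to what is asked for below. The response comparison with the prior regimen shares the selection and could carry the same caveat.

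**Conclusion.** The concern holds. Eligibility selects on poor outcome under prior rituximab, on-study TTP is unrestricted, there is no concurrent control, and the plan gives no caveat. Excluding 1 therefore shows that two medians differ in enrolled subjects, not that adding lenalidomide prolongs TTP.

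Neither the size nor the sign of the bias is fixed by the documents. It ranges from negligible (high correlation, loose cap) to more than the doubling the plan is powered for (independence, tight selection, no decline), and a large enough later-line decline reverses it. Confidence is high in the qualitative point; the figures are only as good as their assumptions. The primary objective, response rate, is not affected.

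**What to change.** 1. In Section 8, replace the significance sentence with: *The ratio of medians and its 95% CI will be reported descriptively; because eligibility selects early failure on prior rituximab, a ratio above 1 is not by itself evidence of benefit.*
2. State that the power figures refer only to detecting a difference between the two medians in enrolled subjects, not a lenalidomide effect, or replace them with the expected interval width.
3. Optionally, add a sensitivity range over the unselected median, the within-patient correlation and the later-line decline.
4. While editing, state the start date of prior-regimen TTP, and say which of the two TTP definitions in Section 7.9 (from first protocol therapy or from first rituximab) is the numerator. This is a clarification and not the basis of the finding.

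The cost is wording in the statistical plan and the loss of one formal significance claim on objective 2.2.1. No extra patients or data are needed, since the planned ratio already requires the prior-regimen dates.
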